#### 2. To evaluate the safety of rapid induction:

Adverse events will be assessed using an adverse events checklist to be completed at the conclusion of the index visit and at each study visit. Physiologic measure (vital signs) and objective measures of level of awareness (agitation-sedation) will be repeatedly assessed during the index visit (as discussed in Secondary Endpoint 1).

#### 3. To assess the duration of effect of BUP 32mg SL on treating opioid withdrawal and craving (days 1-3).

We will generate appropriate descriptive statistics using the aforementioned validated objective, subjective, and physiologic measures of opioid withdrawal, craving, and drug effects on days 1-3. We will generate proportions for the number of participants who report withdrawal, report craving, have objective signs of withdrawal, return to use of other opioids, and/or require prescription for BUP on days 1-3 and estimate the time to occurrence and confidence intervals for these events.

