## 4 Study Design and Endpoints

### 4.1 Description of Study Design

This is an open-label, single arm, single site feasibility and acceptability study in which 35 ED patient-participants who have untreated moderate to severe OUD and are experiencing opioid withdrawal (COWS score  $\geq 8$ ). will receive treatment in the ED with a loading dose of BUP 32mg SL (administered in divided doses) at their index visit. We will assess the feasibility, acceptability, safety, and utility of this intervention and provide preliminary data on the effect on opioid withdrawal, craving, and sedation as well as additional patient-level outcomes (engagement in treatment, drug use, quality of life, healthcare utilization).

The first assessment will occur in-person in the ED at the index visit (day 0), and 4 additional appointments will be scheduled: 3 research visits and one follow-up care appointment with an OUD provider. Research assessments will be conducted in-person at clinical research space on Bellevue/NYULH campus on days 1-3, and by phone on day 30. Patients will be provided with appointment reminder cards with the time and location of their next appointment, and the contact information for the research study team. At the conclusion of their day 3 visit, participants will be given a prescription for BUP SL 16mg per day with a quantity sufficient to last until their scheduled clinical follow up appointment for ongoing treatment. The prescription will be provided earlier, at the day 1 or day 2 research visit, if the participant reports opioid withdrawal and/or craving and has objective signs of withdrawal at that time.

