### **6.9.4 Dosing and Administration**

All participants will receive a total dose of BUP 32mg sublingually in divided doses during the index ED visit. After the participant has received a total of 8mg (as a single dose or in divided doses), BUP SL 24mg will be administered (i.e., 8mg + 24mg, or 4mg + 4mg +24mg). A dose of up to BUP 8mg SL may be administered by the clinical provider prior to enrollment of the patient-participant (i.e., given clinically, not as a research procedure).

After pre-medication assessments are complete and the participant is confirmed to have a COWS of  $\geq 8$ , the participant will be given BUP SL to reach a dose of 8mg. Starting 30 minutes after BUP administration, the participant will be reassessed for withdrawal severity and any adverse events. As long as there are no unexpected significant adverse events, an additional BUP 24mg SL will be administered. Then, participants will be monitored and reassessed every 30 minutes for a period of at least 90 minutes after receiving the last dose of BUP.

Participants will return on days 1, 2, and 3 for research visits. At those visits, participants will be assessed for opioid withdrawal using the COWS scale. On the first day that the participant has objective signs of opioid withdrawal (via COWS), the [name], who is a licensed physician with an X-waiver for BUP prescription, or another study clinician (with the appropriate license and X-waiver) will electronically send a prescription the participant's preferred outpatient pharmacy for a daily dose of BUP 16mg (BUP or BUP/NX 8/2mg: two SL) to start immediately. Participants will be prescribed a quantity sufficient to ensure medication coverage until the date of their appointment for ongoing treatment with a (non-study) OUD treatment provider. Participants who do not exhibit opioid withdrawal at any of the visits on days 1-3, will be given a prescription upon completion of the day 3 visit with instructions to self-administer upon emergence of symptoms of opioid withdrawal or craving.

All participants will receive a referral to be seen by a provider experienced in treating OUD. Thereafter, continued treatment and specific daily dosage of BUP-NX will be a joint decision between the study participant and the healthcare provider.

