### **7.4.3 Intermediate Research Visits**

#### **7.4.3.1 Research Visits (In person, Days 1-3, 30-60 minutes)**

- Participants will complete assessments of withdrawal, craving, and substance use in-person daily for 3 days. The visits will occur either at the ED or at other clinical research space on Bellevue/NYU campus. In light of the health safety risks associated with the COVID-19 pandemic, interviews may be conducted remotely, rather than in-person, using an approved, secure audio or audio-video connection (e.g., telephone, Cisco Webex) from a setting offering adequate privacy. Participants will be advised that they may disconnect their video feed.
- Participants will assess themselves for symptoms of opioid withdrawal using subjective scales
- At the first visit (Day 1-3) in which the participant has objective signs of withdrawal, the participant will be provided with a prescription for BUP. If the participant does not have objective signs of withdrawal by the Day 3 visit, the prescription will be written at the conclusion of that visit. The prescription will be electronically sent to the participant's pharmacy for BUP or BUP/Nx 8/2mg: 2 films/tabs taken SL daily for each day, starting immediately, with a quantity sufficient to last until the scheduled appointment for

Study Number: s19-01700

Version: 7.0

Version Date: 08/01/2022

ongoing treatment)

- Participants will be assessed for adverse events, which will be recorded and reported.

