##### ***Unscheduled Visit***

If a patient is experiencing objective signs of withdrawal outside the hours of one of their research visit appointments, they may present to the Emergency Department for treatment. They will be asked to report this visit to the study team. The PI may be contacted 24 hours a day, seven days a week.

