### **8 Assessment of Safety**

#### **8.1 Specification of Safety Parameters**

### **8.1.1 Definition of Adverse Events (AE)**

An **adverse event** (AE) is any symptom, sign, illness or experience that develops or worsens in severity during the course of the study. Intercurrent illnesses or injuries should be regarded as adverse events.

Abnormal results of diagnostic procedures are considered to be adverse events if the abnormality:

- results in study withdrawal
- is associated with a serious adverse event
- is associated with clinical signs or symptoms
- leads to additional treatment or to further diagnostic tests
  - Note that the existing clinical protocol for the initiation of treatment with BUP in the Bellevue ED includes instructions for patients to return to the ED in some circumstances, including for repeat assessment, for social work or care management or referral assistance, for subsequent dose and/or prescription of BUP, for early return of withdrawal symptoms, etc. If return to the ED is for one of these reasons, it will not be considered an AE.
- is considered by the investigator to be of clinical significance

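### The Day 2-3 score summaries for duration of the 32 mg effect include scores taken after further buprenorphine, so the loading dose can look longer-lasting than it is

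*Combined protocol and SAP*

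**What the plan says.** Section 3.2 makes the duration of the 32 mg effect on withdrawal and craving over Days 1-3 a secondary objective. Section 5.1.2 (Secondary Endpoint 3) serves it in two ways. The first is "descriptive statistics using the aforementioned validated objective, subjective, and physiologic measures of opioid withdrawal, craving, and drug effects on days 1-3". The second is a set of event proportions: reported withdrawal, reported craving, objective signs, return to other opioids, "and/or require prescription for BUP on days 1-3 and estimate the time to occurrence and confidence intervals for these events". Section 10.1 lists withdrawal and craving scores and time to next buprenorphine dose as separate secondary outcomes.

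Re-treatment inside the same window is part of the design:

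- Section 4.1 moves the buprenorphine prescription forward to Day 1 or Day 2 "if the participant reports opioid withdrawal and/or craving and has objective signs of withdrawal at that time".
- Section 6.9.4 sends that prescription "for a daily dose of BUP 16mg (BUP or BUP/NX 8/2mg: two SL) to start immediately". Those with no withdrawal at any of the three visits "will be given a prescription upon completion of the day 3 visit with instructions to self-administer upon emergence of symptoms".
- Section 7.4.3.1 keeps scoring everyone: "Participants will complete assessments of withdrawal, craving, and substance use in-person daily for 3 days".
- Under Unscheduled Visit (Section 7.4.4), participants with objective withdrawal between visits are told "they may present to the Emergency Department for treatment". Section 8.1.1 notes that the existing clinical protocol foresees returns "for subsequent dose and/or prescription of BUP, for early return of withdrawal symptoms, etc".

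Neither Section 5.1.2 nor Section 10.1 says how to treat a score recorded after the next buprenorphine dose.

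**The concern.** Re-dosing is triggered by loss of the effect being measured, so the contamination is selective. The scores that change on Days 2 and 3 belong to the participants in whom 32 mg failed earliest. If the new buprenorphine works, those failures are recorded as low withdrawal and craving scores and credited to the loading dose.

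Whether 32 mg can bridge a patient to follow-up is the rationale for the dose (Section 2), and the results are meant to be compared with benchmark data and to inform larger studies (Section 10.1). A flattering duration figure would carry forward into that planning. The exploratory link in Section 5.1.3 between initial response and duration of effect names no duration measure. It would have the same problem if it used these scores.

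**Working it through.** The plan gives no re-dosing rate, no post-re-dose scores, no power calculation and no target effect, so there is no figure of its own to reproduce. What follows is an illustration with assumed inputs.

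**Inputs from the documents.** Enrolment is n = 35 (Section 6.6), with a goal of 30 completers (Section 6.4). First dosing requires COWS of at least 8 (Section 6.9.4). Near-complete relief is COWS below 3 (Section 5.1.2, Secondary Endpoint 1).

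**Assumptions.** k participants are re-dosed after the Day 1 visit, a share f of them respond, and each responder's COWS falls by d. Two drops are used: 8 to 2 (d = 6) and 5 to 2 (d = 3). The lower start is included because Section 6.9.4 sets no COWS cut-off for re-dosing.

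**Shift in the Day 2 mean** = k × f × d / n. For example, 7 × 1 × 6 / 35 = 1.20.

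| Case | f | k = 4 | k = 7 | k = 11 |
|---|---|---|---|---|
| n = 35, d = 6 | 0.5 | 0.34 | 0.60 | 0.94 |
| n = 35, d = 6 | 1 | 0.69 | 1.20 | 1.89 |
| n = 35, d = 3 | 0.5 | 0.17 | 0.30 | 0.47 |
| n = 35, d = 3 | 1 | 0.34 | 0.60 | 0.94 |
| n = 30, d = 6, all k attend | 0.5 | 0.40 | 0.70 | 1.10 |
| n = 30, d = 6, all k attend | 1 | 0.80 | 1.40 | 2.20 |

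With f = 0 every entry is 0. A same-day proportion in withdrawal, if reported, falls by 1/35 = 2.9 percentage points per relieved participant. A proportion read as ever in withdrawal by that day is not biased by study re-dosing.

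**Day 3 as a mixture.** Suppose those still covered score 2, and re-dosed participants would score 8 untreated but score 2 after re-dosing. The planned Day 3 mean is then 2.0 whatever share was re-dosed. Without re-dosing it would be 0.1 × 8 + 0.9 × 2 = 2.6 at 10%, 0.3 × 8 + 0.7 × 2 = 3.8 at 30%, and 0.6 × 8 + 0.4 × 2 = 5.6 at 60%. In this case the summary cannot tell a dose that held in 90% from one that held in 40%.

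**Is splitting enough?** Take 7 of 35 re-dosed at COWS 8, with the other 28 averaging 3 on Day 2:

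- Pooled, all seven relieved: (28 × 3 + 7 × 2) / 35 = 98 / 35 = 2.8.
- Pooled, half relieved (the seven average 5): (84 + 35) / 35 = 3.4.
- Not re-dosed only: 3.0.
- Pre-re-dose score carried forward: (84 + 56) / 35 = 4.0.

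With full relief the pooled mean is lower than the mean in those still covered by 32 mg. Dropping the seven gives 3.0, which hides them. The cumulative result shows them: 7/35 = 20.0% (exact 95% CI 8.4% to 36.9%). For k = 4 it is 11.4% (3.2% to 26.7%), and for k = 11 it is 31.4% (16.9% to 49.3%).

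**The word require.** Everyone without earlier withdrawal gets a prescription at the end of Day 3. If that routine prescription counted as required, the proportion would be 100% of Day 3 attenders by design.

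**The case against.** The strongest reply is that the better analysis is already planned. Section 5.1.2 includes time to occurrence of withdrawal and of needing a prescription, and Section 10.1 lists time to next buprenorphine dose. These record each failure at first occurrence, before a study prescription can mask it, and a reader would see them beside the scores. The study is also a descriptive pilot with no test or decision rule on the Day 2-3 means, and pooling is inferred from silence rather than stated.

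Much of this stands. The event analyses are a real partial safeguard, and the duration objective does not rest on scores alone. But they do not change what enters the score summaries, and nothing names them as the lead duration result. An unconditional Days 1-3 summary of participants who are all still being scored is most naturally read as pooled, and a descriptive statistic can still describe the wrong thing.

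It is also fair that the size is assumed. The small high-dose studies in Section 2.1.2 report suppression of about 72 hours or longer, so re-dosing could be rare; at d = 6 each fully relieved participant then moves the mean by only 6/35 = 0.17. The prescription must be collected from an outpatient pharmacy, so uptake by the next visit is not assured. The carried-forward 4.0 is itself an assumption about untreated scores. Finally, other opioid use has an uncertain effect on scores: buprenorphine may block it (Section 2.1.3, Safety), or the combination may precipitate withdrawal and raise scores (Section 7.5.1). The net direction is therefore likely, not certain.

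**Conclusion.** The concern holds, with medium confidence, and should be corrected before analysis. As written, the Day 2-3 withdrawal, craving and drug-effect summaries include scores taken after re-dosing in those whose loading dose wore off, and they can overstate duration. For 4 to 11 of 35 re-dosed and half to all relieved from COWS 8 to 2, the Day 2 mean is understated by 0.3 to 1.9 points; from 5 to 2, by 0.2 to 0.9; with 30 attending and an 8-to-2 fall, by 0.4 to 2.2. It is 0 if the prescription is not taken or does not work. All of this rests on assumed re-dosing rates and responses.

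The primary endpoint is fixed at the index visit and is unaffected. Day 1 scores and time to first objective withdrawal are not biased by the study prescription, because objective signs must be present at the visit before it is given early. Unscheduled treatment in the emergency department before a visit remains a separate route by which scores could be altered.

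**What to change.** 1. Name the planned time-to-occurrence analyses as the main duration result: time to first objective withdrawal and time to next buprenorphine dose, with buprenorphine given in the emergency department counted as a dose. Report cumulative proportions by Day 1, Day 2 and Day 3 with confidence intervals.
2. Report scores recorded after re-dosing or other opioid use separately from the 32 mg summary, and print the number already re-dosed beside it. This should accompany item 1, not replace it, because those left are the ones in whom the effect lasted. A row carrying the last pre-re-dose score forward is optional, as is a composite of withdrawal, re-dosing and opioid use.
3. State that the routine prescription at the end of Day 3 marks the end of observation and is not a required prescription.

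The cost is analysis wording. COWS, timeline follow-back, the non-study services form, prescriptions and record abstraction are already planned sources (Sections 1.1.1 and 4.2). The downsides are a possibly less favourable duration figure, fewer scores in the Day 2-3 summary of the 32 mg dose, and a little more analysis.

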#### **4. To assess patient acceptability**

Process data, including reasons for non-participation in some or all aspects of the study/clinical procedures, as well as self-reported measures of treatment satisfaction, good/bad treatment effects, and other patient experience domains (collected at each study visit/encounter) will inform acceptability.

#### **5. To explore treatment effect**

To provide preliminary treatment effect data, we will assess outcomes using measures employed in our other studies, such as linkage to treatment, quality of life, and additional patient-level outcomes (drug use, overdose events, healthcare use) at 30 days.

Preliminary data of treatment effect using outcomes measures employed in our other studies will be collected and assessed. We will explore the effect on initial linkage to and engagement in addiction treatment, quality of life and functional outcomes, and additional patient-level outcomes (drug use, overdose events, healthcare use), including but not limited to the following:

- a. the proportion and confidence intervals of participants of patients engaged in treatment at 30 days, with time to initial linkage to treatment assessed secondarily;
- b. changes in self-reported non-medical opioid use over first 30 days using the timeline follow back method;
- c. changes in patient reported outcomes (using scales such as PROMIS GLOBAL-10 and Treatment Effectiveness Assessment (TEA)), self-reported healthcare utilization (non-study health services form) and overdose events.

These measures will be participant self-report of engagement in treatment, confirmed by the treatment provider, or by direct contact with the facility and/or treating clinician and/or through EMR abstraction. Linkage to addiction treatment will be defined as receipt of an encounter for formal addiction treatment after the index ED visit. Engagement in addiction treatment will be defined as enrollment and receiving formal addiction treatment on the 30th day after the index ED visit. Formal addiction treatment will be those treatments consistent with the American Society of Addiction Medicine's (ASAM) level of care (1-4) and will include a range of clinical settings, including office-based providers of BUP or naltrexone, OTPs, intensive outpatient, inpatient, or residential treatments.

##### **5.1.3 Additional Exploratory Endpoints**

We will explore the potential effect of patient-level characteristics on outcomes, including age, sex, fentanyl use, quantity of opioid use (high/low), injection/non-injection. We will explore associations between initial responses (change in withdrawal during the index visit) to duration of BUP treatment effect (as measured on Days 1-3).

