Study Sites	The study will take place in the Emergency Departments at Bellevue Hospital and NYU Langone Health sites including NYULH-Tisch, NYULH-Brooklyn, NYULH-Winthrop, and NYULH-Cobble Hill.
Number of participants	35 participants
Description of Study Agent/Procedure	BUP 32 mg SL (in two doses of 8mg and 24mg)
Key Procedures	Urine or saliva test, administration of BUP 32 mg SL.
Statistical Analysis	Statistical analyses will consist of descriptive analyses and will provide summary tabulations and measures of central tendency, variance, and other distributional properties of the obtained results. Where applicable, we will also conduct cross-tabulations and comparative analyses of variance based on selected key characteristics of the study participants (e.g., sex, age categories, withdrawal scores at baseline).

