#### Exploratory Analyses:

To evaluate participants’ pre-study opioid use characteristics (opioid type [fentanyl or not], averaged daily quantity, route of administration) and other patient-level characteristics to explore their potential effect outcomes.

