## 10 Statistical Considerations

### 10.1 Statistical and Analytical Plans (SAP)

The overall findings of the study will be used to assess the feasibility, acceptability, and utility of initiating a BUP loading dose in ED patients and linking patients to ongoing OUD treatment. Statistical analyses will consist of descriptive analyses for the primary outcome (proportion of participants successfully induced via loading dose), and secondary outcome measures (opioid withdrawal and craving scores, time to next BUP dose, opioid and other illicit drug use, proportion making a successful transition to an outpatient clinic). Measures of central tendency (the mean), and the variability (standard deviation) of the study participant characteristics and for other participant-reported or objectively evaluated measures will also be calculated. Summary tabulations and measures of central tendency, variance, and other distributional properties of the obtained results will be presented. Where applicable, we will also conduct cross-tabulations and comparative analyses of variance based on selected key characteristics of the study participants (e.g., sex, age categories, baseline opioid requirement). This is a pilot study aimed at producing preliminary data which will inform future large-scale studies. Our analyses will be purely descriptive and we will not attempt to show an effect size, thus there is no power calculation for this sample size, it is based on feasibility.

Our a priori hypotheses of the potential effect of patient characteristics on outcomes will be tested in subsequent large scale studies. The outcomes obtained in the proposed pilot study will also be compared with benchmark data based on the results of our previous studies with similar patient populations and other available recent or contemporaneous research and clinical data. Adverse events recorded in the study will be reported using both quantitative tabulations and qualitative descriptions.

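### Opioid quantity is to be explored as high/low and age in categories, with no cut points given, although both can be analysed as measured values

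*Combined protocol and SAP*

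**What the plan says.** The protocol and SAP are one document, and it describes these characteristics in four places.

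- Section 3, Exploratory Analyses, lists the pre-study opioid use characteristics as "opioid type [fentanyl or not], averaged daily quantity, route of administration". Quantity here is an average per day.
- Section 5.1.3 explores "patient-level characteristics on outcomes, including age, sex, fentanyl use" and then "quantity of opioid use (high/low), injection/non-injection". Quantity is now two levels and age is ungrouped.
- The Statistical Analysis entry of the Protocol Summary gives as example characteristics "e.g., sex, age categories, withdrawal scores at baseline".
- Section 10.1 gives "e.g., sex, age categories, baseline opioid requirement" as its examples. Age is again in categories, and baseline opioid requirement stands where the Summary has withdrawal scores.

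The method named in 10.1 is "we will also conduct cross-tabulations and comparative analyses of variance based on selected key characteristics of the study participants", and the Summary says the same. Neither place mentions correlation, regression or a plot. No boundary between high and low quantity is given, and neither the number nor the limits of the age categories.

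**The concern.** Replacing a measured value by a group label does two kinds of harm, even when only one characteristic is examined.

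The first is lost precision. Everyone on the same side of a boundary is treated as alike, so a gradient across the range is harder to see. With 35 participants there is little precision to spare.

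The second is an open choice. The study is open-label with one arm, and the data can be looked at before the high/low boundary is drawn. Different boundaries can give different pictures, and the reader cannot tell how the reported one was picked. This harm needs no distributional assumption.

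Section 10.1 says the pilot's preliminary data will inform larger studies and leaves the hypotheses about patient characteristics to them. What can usefully carry forward is the shape and size of each association. A contrast between two undefined groups is hard to compare with other data.

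**Working it through.** **Inputs from the plan.** 35 enrolled, with a goal of 30 completing (Section 6.4). Quantity in two levels, no cut point (5.1.3). Age in an unstated number of categories (Summary, 10.1). Section 10.1 gives no power, significance level or effect size, so there is no figure of the plan's own to reproduce.

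**Assumptions added here.** The shape of the predictor, a linear relation with the outcome, and the position of the cuts. None is in the documents, so a range is shown.

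**Step 1. Two groups, normal predictor.** With a share p below the cut c, and φ the normal density, the efficiency relative to the continuous value is φ(c)² / [p(1 − p)]. At the median this is 0.3989² / 0.25 = 0.637 (that is, 2/π), a loss of 36.3%. Then 35 × 0.637 = 22.3, and for 30 completers 30 × 0.637 = 19.1. The standard error rises by a factor of 1/√0.637 = 1.25.

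| Split | Efficiency | Loss | 35 act like |
|---|---|---|---|
| 50/50 | 0.637 | 36.3% | 22.3 |
| 40/60 | 0.622 | 37.8% | 21.8 |
| 30/70 | 0.576 | 42.4% | 20.1 |
| 20/80 | 0.490 | 51.0% | 17.1 |

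**Step 2. Several equal groups, normal predictor.** The efficiency is the between-group share of the predictor's variance.

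| Groups | Efficiency | Loss | 35 act like |
|---|---|---|---|
| 3 | 0.793 | 20.7% | 27.8 |
| 4 | 0.861 | 13.9% | 30.1 |
| 5 | 0.897 | 10.3% | 31.4 |

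These figures score each group at its mean. An analysis of variance that ignores the order of the groups would be less sensitive to a trend.

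**Step 3. Median split, other shapes.** The efficiency is the squared correlation between the predictor and its high/low indicator (2,000,000 simulated draws).

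| Predictor | Efficiency | Loss |
|---|---|---|
| Uniform | 0.750 | 25% |
| Lognormal, log-SD 0.5 | 0.516 | 48% |
| Exponential | 0.480 | 52% |
| Lognormal, log-SD 1 | 0.273 | 73% |

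The skewed rows compare with a straight line on the raw scale. Ranks are evenly spread, so the uniform row is the fair comparison if the relation is linear in ranks: a loss of 25%, and 35 × 0.75 = 26.

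**Step 4. What this does to a visible signal.** Simulation with n = 35, two-sided 5% level, normal predictor, 40,000 replicates. The correlations are assumed. The plan does not test these associations, so this only illustrates scale.

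| True correlation | Detected, continuous | Detected, median split |
|---|---|---|
| 0.3 | 42% | 28% |
| 0.4 | 68% | 47% |
| 0.5 | 88% | 69% |

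**The case against.** The strongest reply is that these analyses are exploratory and descriptive. Section 10.1 says there is no power calculation and no attempt to show an effect size, so power figures answer a question that the plan does not ask. That stands, and it is why the point is minor. It does not favour grouping, because a descriptive analysis gains most from showing the data as measured.

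The plan also does not forbid a continuous analysis. Section 3 keeps the daily quantity, 5.1.3 lists age ungrouped, the lists in the Summary and 10.1 are only examples, and 10.1 promises means and standard deviations of participant characteristics. This is fair, but the only methods named for relating characteristics to outcomes work on groups, and high/low is explicit for quantity.

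Two practical objections narrow the fix. No section gives a common unit across opioid types, so a single slope on raw quantity may mean little. Several outcomes are binary, such as successful induction and engagement at 30 days, and a scatter plot suits them poorly. If every participant succeeds, as Section 3.1 hypothesises, the primary outcome has no variation to relate to anything. Ranks, and displays by outcome group, meet the first two. Nothing meets the third, and grouping would not help there either.

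A reader might infer from the cross-tabulations and analyses of variance that baseline withdrawal will be cut as well. The documents do not say so. The Summary calls it scores, in the same list that says categories for age, 10.1 names another variable in that position, and 5.1.3 omits it.

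**Conclusion.** The point holds for opioid quantity, where two levels are explicit, and for age, where categories appear in the Summary and 10.1 but not in 5.1.3. In neither case is a boundary given.

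The loss is about 36% only for a median split of a roughly normal predictor with a linear effect. Under the other assumptions shown it runs from about 10% (five equal age groups) to over 50% (a skewed quantity on its raw scale). An uneven split of a normal predictor costs more than a median split.

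It would be tempting to say that the study throws away about a third of its information. The documents do not support that. They fix neither the cuts nor the number of groups, and the loss falls on each exploratory association separately. The primary proportion and its confidence interval do not use these variables. This is an improvement worth making, of low severity.

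**What to change.** In 5.1.3, the Summary and 10.1, state that average daily quantity and age will be analysed as continuous or ranked values.

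- **Numeric outcomes:** a scatter plot and a rank correlation with its 95% interval.
- **Binary outcomes:** the distribution of the predictor in each outcome group, or the difference in medians with its interval.
- **Baseline withdrawal:** keep it as a score and say so. Align the example lists in the Summary and 10.1, which differ in their third entry.
- **Categories:** for display in tables only, with the boundaries fixed before the data are examined, for example at the median.

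The cost is wording, provided that quantity is recorded as a number, as Section 3 implies. No new visit, measure or participant is needed. There is one small downside: if quantities are recorded in units that differ by opioid type, they should be ranked or summarised within type, and a type with few users will then support description only.
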